6.1 Study Visit Summaries

6.2 Screening:

The subject will provide written informed consent prior to screening. The study will be explained to each subject. An Informed Consent Form (ICF) will be signed by each subject before study participation as mandated by FDA regulations and the institutional review board (IRB). (See Appendix B) A blank copy of the IRB approved informed consent form must be kept on-site and by Tactile Medical™. A copy of the ICF will be given to the subject to read and take home to consider, if they prefer. All the subject's questions must be answered prior to signing the ICF. Research procedures cannot be performed until the subject provides consent. The signed original for each subject must be kept in the subject's research records. A copy of the signed consent form will be given to each subject.

After informed consent is obtained, screening will commence. (See Appendix C: Screening Form) The subject's head and neck measurements will be taken to assist with garment size selection. For subjects with a tracheostomy, the fit will be accessed further to ensure that the garments do not interfere with their tracheostomy. The head and neck garment measuring guide is included in Appendix A. Should the head and neck measurements indicate the garment will not fit, no further information will be obtained and the subject will be withdrawn. After the garment fit has been confirmed the remaining inclusion and exclusion criteria will be evaluated to ensure that the subject meets all entrance criteria. The subject should not undergo any study specific procedures until after the informed consent process and screening processes are complete.

6.3 Baseline Visit:

The screening and baseline visit can occur on the same day or different days depending on the needs of the subject. At this visit, the subject will undergo the baseline data collection procedures as outlined in the Study Schedule of Activities in section 7.4.

Randomization:

After completing the informed consent process and baseline data collection (including the endoscopy) subjects enrolled at each site will be randomized (1:1) to either the investigational group or wait-list control group via the use of a computer-generated, permuted block program executed by the study biostatistician. Each site will have its own unique randomization list.

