7.2.3.2 Safety (Both Groups) will be evaluated using CTCAE V4.0¹¹

7.2.3.3 Pre and Post treatment Survey (Intervention Group Only): Subjects will complete a pre and post treatment survey. The survey will be administered at the baseline visit and at the end of the intervention.

7.2.4 Swelling/Inflammation (Appendix F):

7.2.4.1 Endoscopy with Modified Patterson Scale: The Patterson Scale evaluates internal edema in the pharynx and larynx. The Modified Patterson Scale, with established face validity, includes anatomical sites that may develop internal edema.¹²

7.2.4.2 Cytokines: The study nurse or phlebotomist will draw blood at baseline and at the 8-week visit. The following inflammatory markers will be assessed: IFN γ TNF- α , TGF- β , IL-1b, and IL-6. MMP-2, MMP-9, and CRP will also be assessed if testing is available.

7.2.4.3 Digital Photography: At the visits outlined in the Study Schedule of Activities table in section 7.4, subjects will have photos taken of their affected areas to evaluate external swelling/inflammation. These photos will be taken according to the standard procedure as outlined in Appendix F.

7.2.4.4 Grading of External Lymphedema: Trained study personnel will complete a physical examination of the head and neck area. Grading will be documented via the Head and Neck Lymphedema and Fibrosis Assessment criteria.¹³

7.2.5 Function (Appendix G):

7.2.5.1 Neck Disability Index (NDI): This 10-item instrument assesses components of daily life that may be affected by neck pain and dysfunction. Items include pain, personal care, lifting, reaching, headache, concentration, work, driving, sleeping, and recreation. Internal consistency of the 10-item scale is adequate ($\alpha = .89 - .92$).^{14,15} Factor analysis identified one dimension. Stability of the instrument also is adequate ($r = .89$). Validity of the NDI was supported by the moderate to strong correlations with self-reported activity improvement following treatment and pain.

7.2.5.2 Voice Handicap Index (VHI): This 30 item instrument taps function, emotion, and physical areas that may be affected by

voice disorders such as those caused by chemo-radiation therapy for HNC.¹⁶ Internal consistency of the 30-item scale is adequate ($r=0.95$).

7.2.5.3 Cervical and Shoulder ROM: These measurements will be taken according to the instructions provided in Appendix G. The measurements will be taken at intervals outlined in the Study Schedule of Activities table (section 7.4).

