Self-care Checklist			weekly		
Safety					
Adverse Events- CTCAEV4.0*			√	√	√
Satisfaction					
Pretreatment survey**		√			
Post treatment survey **					√
Swelling/Inflammation					
Internal- Endoscopy/Patterson Scale		√			√
Digital Photography		√	√	√	√
Grading and Staging*	√	√	√	√	√
Cytokines		√			√
Function					
Range of motion-jaw, shoulder, neck		√		√	√
Patient Reported Outcome- Neck Disability Index		√		√	√
Patient Reported Outcome- Voice Handicap Index		√		√	√
Symptoms					
Vanderbilt H and N Symptom Survey		√		√	√
Lymphedema Symptom Intensity and Distress Scale		√		√	√
Quality of Life					
Linear Analog Self- Assessment		√		√	√

*=safety checks at week 9, 12, &16 for wait-list group opting to use the device

**=intervention group only

8.0 Study Device Accountability (Appendix I):

The site must maintain a device accountability log for the Flexitouch®. Completion of this log will ensure that all study devices are properly tracked and accounted for throughout the study from the time they are received by the institution to the time they are returned to the study sponsor or other designated site. Device location, subject ID assigned, date subject returned to site, controller disinfected, and final disposition (e.g., returned to sponsor, garments discarded) of all Flexitouch® controllers, and garments will be documented.

Tactile Medical™ must also maintain device accountability documenting all shipments and returns of study devices by serial number, date, and person completing the log. Storage locations for the study devices and garments will be secure (i.e., locked and away from other devices) with access restricted only to investigators and authorized research personnel. At the conclusion of the treatment period, the subject will return the Flexitouch® controller to the study site. Garments may be retained by the subject or discarded. Site personnel will return all controllers and any unused garments to Tactile Medical™ at the completion of the study.

9.1 Risk Analysis and Adverse Events:

9.2 Risk Analysis: The subjects enrolled in the study are not expected to be at any higher or additional risk than those who undergo in-clinic CDT. There is minimal risk with CDT. These risks may include but are not limited to increased swelling and pain.

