12.3 Statistical Analysis Plan

Minimization of Bias: Stratified randomization to the study groups within each study site will be conducted. Given that this is a wait list/control design, blinding is not possible. Each subject will be assigned a study ID number that will be used for identification purposes in the data. The study statistician who will have no contact with any study participants and will conduct all analyses.

Missing Data: Randomly missing item responses within the study survey measures will be handled as specified by the measure developers. Nonrandom missing visit data are informative for this study (i.e., may speak to feasibility) – no imputation will be conducted.

Interim Analysis: Given that this is a feasibility study, no interim analyses will be conducted. The primary reason for early stoppage would be adverse events.

Aims:

Primary Aim: To determine the feasibility of use of the Flexitouch® Head and Neck Garment, specifically a) to evaluate implementation fidelity (adherence) and barriers to implementation fidelity, b) to establish safety, and c) to assess satisfaction.

Secondary Aim: To determine the preliminary efficacy of Flexitouch® Head and Neck Garment compared to a wait-list control for the following outcomes: a) reduction in swelling/inflammation, b) function (range of motion cervical, jaw, and shoulder), c) symptoms, and d) quality of life.

12.4 Statistical Analyses:

Aim 1 (feasibility): Descriptive statistics (percentages) will be used to summarize adherence to the protocol, barriers, adverse effects, and ratings of satisfaction. Comparison of the rates observed within each of the study groups will be compared using likelihood Chi-Square tests however it is expected that $\geq 75\%$ of the total number of participants enrolled in the study as a whole will complete the study. At the end of the study, it is expected that participants in the investigational group will report acceptable levels of satisfaction with the device, as indicated by 80% rating the satisfaction items above neutral.

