Aim 2 (preliminary efficacy): Descriptive and graphical summaries of the measures at each time of assessment will summarize the overall and group changes in each of the outcome measures over the 8-week study period for each of the groups. Mixed effects general linear models will be used to generate estimates of the interactive effect of the Flexitouch® Head and Neck Garment and time in the study on the primary outcomes. Such an interaction effect would be indicate, for example, larger reduction in symptoms for the intervention group than that observed in the wait list control over the same time period. Bias-corrected effect sizes of garment use on the respective changes will be generated from each of the outcomes. While this study is a preliminary study of efficacy and effect sizes, a maximum alpha level of .05 will be used for statements of “statistical” significance.

Safety Analysis: During the time any participant is using the device, safety checks (Adverse Evetns-CTCAEV4.0, B/P, Pulse, and staging) will be made at defined intervals as noted in section 7.3.

Determination of Sample Size: The primary rationale for study size is the proposed funded time of this study and the number of potential subjects that could be recruited during that time. This is not a hypothesis testing study rather it is a preliminary feasibility and efficacy study for generating observed effect sizes. Nevertheless, samples of 20 individuals in each group (total=40) who successfully complete the 8-week protocol will provide 80% statistical power to detect a differential level of change of approximately 0.9SD (effect size). In other words, assuming a baseline Neck Disability Index (NDI) of 20 (SD=10) and that the wait-list control group demonstrates no change from baseline, a reduction in mean NDI to 11 in the garment group would indicate a statistically significant difference (2-sided alpha-0.05). We have no evidence to hypothesize differences of that magnitude however; we do believe that our sample size will provide sufficient data for estimating reasonable effect estimates for future studies.

13.0 Compensation:

Subjects may be compensated for time and travel at an amount determined by each site.

14.0 Publication Plan:

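### Aim 2 is estimated as a garment-by-time interaction on changes with no stated baseline adjustment; a baseline-adjusted week-8 contrast would usually be more precise from the same data, at almost no cost

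*Combined protocol and SAP*

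**What the plan says.** Section 12.4, Aim 2: "Mixed effects general linear models will be used to generate estimates of the interactive effect" of the garment and time in the study. The same paragraph adds: "Bias-corrected effect sizes of garment use on the respective changes will be generated from each of the outcomes". Neither 12.3 nor 12.4 mentions a baseline covariate, a common baseline mean or a week-8 contrast, and neither rules them out. Whether time is linear or categorical is not said.

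Section 12.4, sample size: the number of subjects follows from the funding period and expected recruitment, and the purpose is to obtain effect sizes for later studies. With 20 completers per group, 80% power is stated for a differential change of about 0.9 SD, illustrated by a 9-point NDI difference (20 to 11) with a baseline SD of 10.

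Section 6.3: "After completing the informed consent process and baseline data collection (including the endoscopy) subjects enrolled at each site will be randomized (1:1" to the two groups. In the section 7.4 schedule, however, the first column joins randomisation to screening and stands before the baseline column.

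Section 7.4: the row "Patient Reported Outcome- Neck Disability Index" is marked at baseline, week 4 and week 8, and the row "Internal- Endoscopy/Patterson Scale" at baseline and week 8 only. For cytokines, section 7.2.4.2 says that staff "will draw blood at baseline and at the 8-week visit". External grading is marked at screening, baseline and weeks 1, 4 and 8.

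Section 7.2.5.1, on the NDI: "Stability of the instrument also is adequate", with r = .89 and no retest interval given.

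**The concern.** An interaction in a model that gives each group its own baseline mean subtracts the whole baseline value from the week-8 value. Unless the two are very highly correlated, this carries baseline noise into the estimate. Regressing on baseline removes only the part that predicts week 8.

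What is at stake is the width of the intervals around the Aim 2 effects, which the protocol presents as the product of the study. The sample size is fixed by money and time, so the analysis is the main remaining way to narrow those intervals, and the baseline values will be in the database anyway.

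**Working it through.** **Inputs from the documents.** 20 completers per arm, two-sided alpha 0.05, SD 10, difference 9 points (12.4); 1:1 allocation after baseline (6.3); NDI stability .89 (7.2.5.1). **Assumed:** the correlation rho between baseline and week 8, taken as 0.3, 0.5, 0.7 and 0.89, and the ratio k of the week-8 SD to the baseline SD (1, 0.8, 1.2).

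**1. The plan's own figure.** SE = 10 × √(2/20) = 3.162, and 9/3.162 = 2.846. Power is Φ(2.846 − 1.960) = 81.2% by normal approximation and 79.2% by noncentral t with 38 df. The stated 80% reproduces.

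**2. The correlation behind that example.** It uses 10 as both the baseline SD and the SD of change. With equal SDs the SD of change is 10√(2(1 − rho)). Setting this to 10 gives rho = 0.5.

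**3. Variance ratio, adjusted to change score, equal SDs.** The change contrast has variance proportional to 2(1 − rho) and the adjusted contrast to (1 − rho²), so the ratio is (1 + rho)/2. Estimating the slope multiplies it by 1 + 1/(2n − 4): 1 + 1/36 = 1.0278 at n = 20 and 1 + 1/26 = 1.0385 at n = 15. The equivalent n is 20 divided by the ratio. Half-widths use SD 10 at both visits.

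| rho | ratio, n = 20 | change-score n per arm for equal precision | 95% CI half-width, NDI points: change → adjusted | ratio, n = 15 |
|---|---|---|---|---|
| 0.3 | 0.67 | 30 | 7.6 → 6.2 | 0.68 |
| 0.5 | 0.77 | 26 | 6.4 → 5.6 | 0.78 |
| 0.7 | 0.87 | 23 | 5.0 → 4.6 | 0.88 |
| 0.89 | 0.97 | 21 | 3.0 → 3.0 | 0.98 |

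The n = 15 column takes 75% of 20 without replacement. Section 12.4 expects at least 75% of the "participants enrolled in the study as a whole will complete the study".

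**4. Unequal SDs.** The ratio is k²(1 − rho²)/(1 + k² − 2k·rho) × 1.0278. In the same order of rho it is 0.52, 0.59, 0.65 and 0.63 at k = 0.8, and 0.78, 0.90, 0.99 and 1.01 at k = 1.2.

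**5. Worst case.** Before the slope factor, the change-score variance exceeds the adjusted variance by a term proportional to (1 − k·rho)², which is never negative. The loss is therefore bounded by the slope factor: 2.8% at 20 per arm, 3.8% at 15. The largest ratio in step 4 is 1.012. With equal SDs and n = 20, adjustment stops helping at rho = 2/1.0278 − 1 = 0.946.

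**6. Does the mixed model recover the gain unaided?** Generalised least squares with complete data, rho = 0.5 and SD 10 gives SE 3.162 with free baseline means and 2.739 with a common baseline mean, for visits 0/8 and for 0/4/8. The variance ratio is 0.75, which is (1 + rho)/2 before the slope factor. A decaying correlation (0.7, 0.7, 0.5) for 0/4/8 gives the same result. The week-4 visit does not supply the gain; the constraint or covariate does.

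**7. Simulation.** In 20,000 trials at rho = 0.5 with a 9-point difference, power was 78.9% for the change score and 88.2% for the adjusted contrast. This agrees with the formulas (79.2% and 88.4% by t).

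**The case against.** The strongest reply is that this is a preference about efficiency. The planned interaction is valid, the text does not exclude adjustment, and a mixed model with a common baseline mean would fit the wording and already deliver the gain. Aim 2 is the secondary aim of a pilot. All of that stands, and it is why the point is an improvement and not a fault.

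The size of the gain also rests on assumed correlations. At .89 the NDI interval does not visibly narrow. That stands too, although .89 is a stability coefficient over an unstated interval and not a correlation across eight weeks of a trial.

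Three further objections shape the remedy:

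- Equal expected baselines hold for all randomised subjects, not necessarily for those retained. One withdrawal trigger in 5.3.3 depends on diary-recorded device use, and only the intervention group keeps a diary. Section 5.3 replaces subjects withdrawn for non-adherence. A common baseline mean is not guaranteed in a completers-only analysis.
- An adjusted effect size needs a named SD. At rho = 0.5 with SD 10, 9 points is 0.90 baseline SDs but 9/8.66 = 1.04 residual SDs.
- For measures taken at weeks 0, 1, 4 and 8, such as grading, a linear-time interaction can match or beat the common-baseline contrast (SE 2.23 against 2.26 at rho 0.7, SD 10, compound symmetry), but only if the trend is truly linear.

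A reader might infer that the planned estimate is biased or that the power statement is wrong. The documents support neither: randomisation protects the estimate, and the 80% reproduces.

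**Conclusion.** The point holds as a nearly free gain in precision. With 20 per arm and equal SDs, adjustment removes about 33%, 23%, 13% and 3% of the variance at rho 0.3, 0.5, 0.7 and 0.89. The gain is larger if week-8 values vary less than baseline values, and it can vanish if they vary more. The documents point to two different places in that range, 23% from the sample-size example and 3% from the stability coefficient, and settle on neither. It would be too strong to say that the trial forgoes a quarter of its precision. What can be said is that the possible loss is small and bounded, while the possible gain is material. The figures assume complete data, a linear relation to baseline and conventional fitting with free baseline means. If the study statistician already intends a common baseline mean, only a clarifying sentence is needed.

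**What to change.** In section 12.4, Aim 2:

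- State that each continuous outcome is analysed with its baseline value as a covariate: ANCOVA where it is measured only at baseline and week 8 (cytokines, on a log scale if skewed), and a mixed model where there are several follow-up visits (NDI, Voice Handicap Index, range of motion, symptom surveys, quality of life).
- Report the week-8 group contrast with a 95% CI.
- Include external grading, and endoscopy ratings if they are grades, in a baseline-adjusted form suited to the scale, for example an ordinal model.
- Allow a common-baseline-mean model as an equivalent option if all randomised subjects are included.
- Name the SD that standardises the bias-corrected effect size, for example the baseline SD and not the residual SD, so that later studies can plan from it.

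In section 7.4, align the first column header with section 6.3, which places randomisation after baseline data collection.

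The cost is wording, about one degree of freedom per outcome, and at worst the small variance loss shown above. No new data or visits are needed.

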5.1 Study Design

This study is an open label, multi-site, stratified by site, randomized, wait list control, pilot study. Vanderbilt University will serve as the multi-site coordinating center.

Within each study site:

5.2 Study Endpoints :

5.2.1 Primary Endpoints: The primary endpoint will occur when subjects complete the 8th week of treatment and provide: a) evaluation of implementation fidelity (adherence) and barriers to implementation fidelity, b) review of adverse events, and c) report satisfaction.

5.2.2 Secondary Endpoints: The secondary endpoints will be a) reduction in swelling/inflammation, b) function (range of motion cervical, jaw, and shoulder), c) symptoms, and d) quality of life.

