5.3 Subject Selection

The study sample will be drawn from patients who have received head and neck cancer therapy and have developed HNL secondary to their cancer treatment.

Patients will be recruited from the head and neck cancer clinic at Vanderbilt University and similar clinics at the other investigational sites(s). The patient must have undergone (or attempted and failed) complete decongestive therapy (CDT), or is unable to access CDT as outlined in the inclusion criteria. Only patients who meet the criteria listed below will be considered for the study. A total sample of 40 subjects (20 per group balanced within each site) will be enrolled and those withdrawn for lack of adherence will be replaced, thus we may enroll up to 50 individuals.

5.3.1 Inclusion Criteria :

- Age \geq 18 years
- A previous diagnosis of histologically defined head and neck cancer
- A diagnosis of head and neck lymphedema
- Must be able and willing to participate in all aspects of the study and provide informed consent prior to study participation
- Complete cancer treatment with no evidence of active cancer; all post-surgical swelling must be resolved.
- The head and neck garments must fit appropriately. For patients with a tracheostomy, the fit will be assessed to ensure that the garments do not interfere with their tracheostomy.
- The subject must have experienced at least one of the following:
 - Completion of phase 1 lymphedema care in the past 8 weeks
 - The inability to participate/complete phase 1 care due to:
 - lack of available therapist/clinic
 - lack of insurance coverage or funding to support cost of care.

5.3.2 Exclusion Criteria: Subjects will be determined to be ineligible for this study if they meet any of the criteria described below :

- Uncontrolled hyperthyroidism or parathyroidism (for which endocrinologist recommends against neck compression)
- Carotid sinus hypersensitivity syndrome
- Symptomatic carotid artery disease, as manifested by a recent transient ischemic attack (within 30 days), ischemic stroke, or amaurosis fugax (monocular visual ischemic symptoms or blindness)
- Symptomatic bradycardia in the absence of a pacemaker
- Internal jugular venous thrombosis, acute or within 3 months
- Increased intracranial pressure or other contraindications to internal or external jugular venous compression
- Acute radiation dermatitis, unhealed surgical scar, unhealed or open wound(s), surgical flap less than 6-8 week post-operative

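### Randomisation is stratified by site, but the Aim 2 model names no site term; if sites differ in change over time, the standard error is too large and the test conservative

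*Combined protocol and SAP*

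**What the plan says.** Section 5.1 gives the design: "This study is an open label, multi-site, stratified by site, randomized, wait list control, pilot study". Section 5.3 plans the balance: "A total sample of 40 subjects (20 per group balanced within each site) will be enrolled". Under Randomization in section 6.3, subjects at each site "will be randomized (1:1) to either the investigational group or wait-list control group via the use of a computer-generated, permuted block program", and "Each site will have its own unique randomization list". Section 12.3 repeats this as a measure against bias: "Stratified randomization to the study groups within each study site will be conducted".

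For Aim 2, section 12.4 states: "Mixed effects general linear models will be used to generate estimates of the interactive effect" of garment and time. It goes on: "Bias-corrected effect sizes of garment use on the respective changes will be generated from each of the outcomes". The section names garment, time and their interaction. It gives no full list of fixed effects, random effects or covariates, does not mention site in any role, and does not define the SD behind the effect sizes. The documents do not state how many sites there will be, or any variance between sites.

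**The concern.** Stratifying by site removes site differences from the comparison of the arms. An analysis that ignores site leaves those differences in the residual, so the reported standard error describes a less precise trial than the one that was run.

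Sites could plausibly differ in how much subjects change. Range of motion, external grading and endoscopy scores are assessed by local staff (section 7.2). Home care is set by each subject's own provider (section 5.4). Eligibility admits both subjects who recently completed phase 1 care and subjects who could not get or complete it (section 5.3.1), and that mix may vary by clinic.

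Section 12.4 gives effect sizes for future studies as the main product of the efficacy part. Intervals wider than necessary, and a standardised effect whose denominator is not stated, both reduce the value of that product.

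**Working it through.** **Inputs from the plan (section 12.4).** 20 completers per group, two-sided alpha 0.05, a difference of 9 NDI points with SD 10 (0.9 SD), and 80% power.

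**Assumed.** The site share *s* of change-score variance is 0 to 30%, with 2 or 4 sites and arms balanced 1:1 within site.

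**Step 1: the plan's own figure.** The noncentrality is 0.9 × √(20/2) = 2.85. With 38 df the t-test has power 79.2%; the normal approximation gives 81.2%. The stated 80% is reproduced. It makes no allowance for site.

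**Step 2: standard error.** Set the total variance of change to 1. Without site, the reported SE is about √(2/20) = 0.316 whatever *s* is. Because the arms are balanced within site, the true SE is √((1 − s) × 2/20): 0.308, 0.300, 0.283 and 0.265 at 5%, 10%, 20% and 30%. The overstatement is 1/√(1 − s), that is 1.026, 1.054, 1.118 and 1.195.

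**Step 3: simulation.** 20,000 trials per setting, 40 change scores each, true difference 0.9 (or 0 for type I error), analysed with and without site.

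| Site share | Reported / true SE without site (2 sites) | Type I error without site (2 / 4 sites) | Power without → with site, 2 sites | Power without → with site, 4 sites | Bias-corrected effect size, total → within-site SD (2 sites) |
|---|---|---|---|---|---|
| 0% | 0.314 / 0.313 | 4.9% / 5.1% | 79.7 → 79.6% | 79.0 → 78.9% | 0.90 → 0.90 |
| 5% | 0.314 / 0.306 | 4.2% / 4.8% | 80.2 → 81.6% | 79.4 → 80.8% | 0.90 → 0.93 |
| 10% | 0.315 / 0.297 | 3.6% / 3.9% | 80.1 → 83.0% | 80.5 → 83.1% | 0.90 → 0.95 |
| 20% | 0.316 / 0.284 | 2.8% / 3.2% | 81.2 → 87.2% | 81.5 → 87.2% | 0.89 → 1.00 |
| 30% | 0.317 / 0.265 | 1.9% / 1.7% | 82.2 → 91.2% | 82.6 → 90.9% | 0.89 → 1.08 |

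With site in the model, type I error stays at about 5% (4.7% to 5.5%). The mean raw difference is 0.90 in every row, with and without site. With unequal sites (14, 11, 9 and 6 subjects) and blocks of 4, bias was again about 0.00 in both analyses.

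**Step 4: which site term matters.** One illustrative repeated-measures data set, with baseline as an outcome, gave a group-by-time estimate of −6.64 in every version. Its SE was:

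| Difference built in between sites | No site term | Site main effect | Site and site-by-time |
|---|---|---|---|
| 8 points in level | 3.00 | 3.00 | 2.83 |
| 8 points in change | 3.43 | 3.43 | 2.83 |

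A difference in level does no harm, because it cancels within subject. A difference in change inflates the SE, and a site main effect alone does not remove it. The SE was also 2.83 with site-by-time when no site difference had been built in, so the step from 3.00 to 2.83 is best read as a chance feature of this one data set.

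**Step 5: effect-size denominator.** Dividing 0.9 by √(1 − s) gives 0.92, 0.95, 1.01 and 1.08, close to the within-site values in the first table. Required sample size goes as 1/d², so 0.95 instead of 0.90 changes a later trial's size by a factor of (0.95/0.90)² = 1.11.

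**The case against.** Section 12.4 names a class of model and the effect to be estimated; it is not a complete specification. A reader might infer that the plan excludes site. It does not: it is silent, and the analyst could still include it. That stands, and it limits the point to an omission in what is written.

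A reader might also infer that the estimated effects are distorted. They are not. The raw difference is the same with and without site, and dividing by the total SD recovers the simulated 0.9 total SD without any site term. The value rises only if the within-site SD is chosen as denominator. That is a legitimate choice, but not the only one; it could make planning too optimistic for a later multi-site trial analysed on the total SD. What stands is that the plan should state its choice.

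Nor do differences between operators as such inflate the error. Constant offsets cancel, many outcomes are self-reported or laboratory measures, and the plan provides for trained graders, standard measurement instructions and staff training (sections 7.2 and 12.2). Only differences in change matter, and the documents report none.

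Finally, 4 sites and four visits would add 3 + 9 = 12 parameters for 40 subjects. These are spread over four visit means, so each contrast loses about 3 degrees of freedom, from 38 to 35. The simulation used a single change score and did not test the larger model directly, so very small sites would need care.

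**Conclusion.** The point holds as a mismatch between design and stated analysis: the trial randomises by site, and the Aim 2 model names no site term. The consequence is lost precision. It is neither bias nor an excess of false positives.

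At an assumed site share of 5% to 10% the loss is small: an SE about 2-5% too large and 1 to 3 points of power. At 20% to 30% it is material: 12% to 20% on the SE and about 6 to 9 points of power. Power without site stays at about 80% or slightly above throughout, so the plan's own target is not undermined.

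The size rests on the assumed share, on 2 or 4 sites, and on arms staying close to balanced within site among those analysed. Severity is modest, because these are secondary aims of a pilot that disclaims hypothesis testing. The change is still worth making because it costs almost nothing.

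**What to change.** In section 12.4, list the terms of the Aim 2 models. Where baseline is one of the repeated outcomes, include site and site-by-time as fixed effects. Where change or baseline-adjusted week-8 values are analysed, a site main effect is enough. If any site may enrol very few subjects, state in advance how such sites will be combined.

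In the same section, state which SD standardises the bias-corrected effect sizes, total or within-site. Reporting the raw difference and both SDs would let later planners use either.

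The cost is a sentence or two of wording and no new data, since each site already has its own randomisation list. Statistically it is one degree of freedom per extra site for each contrast, which in the single-change-score simulation amounts to 0.2 percentage points of power or less if site explains nothing.
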